dyads reported benefits, the finding should be read considering a number of shortcomings such as the small sample, the intervention development at a single center and its delivery by a single nurse researcher.

It is therefore useful to contribute to the debate on the cachexia, so that we can develop reproducible and effective psycho-educational interventions.

Objectives of the Study

Primary objective: to evaluate the feasibility of a psycho-educational intervention on cachexia combined with a physiotherapy intervention on the cancer patient and his caregiver.

Secondary objective: improve the quality of life of patient and caregiver, acceptability of the intervention, adherence to each of the two psycho-educational and rehabilitative components.

What does this study contribute?

There are no studies on psycho-social interventions on dyads associated with rehabilitative interventions to support more functional relationships to the management of cachexia. The two psycho-educational and rehabilitative components have a strong rationale, common objectives and modalities with respect to the care of the patient and the family, compared with the multimodal approaches explored in the literature. We will evaluate the feasibility of the intervention in the population and context studied, estimating the effect of the intervention for a future multicenter efficacy study.

Methodology

Study design

Mixed methods study, non-pharmacological interventional perspective.

Sample and setting

Population of cancer patients with irreversible cachexia and their caregivers assisted by Palliative Care Unit, Azienda Usl - IRCSS of Reggio Emilia. The number of consecutive patients identified is 30.

Inclusion criteria

- Age of 18 years or older
- Good command of the Italian language
- Written informed consent
- Histologically confirmed tumor diagnosis
- Presence of irreversible cachexia and cachexia (ESPEN3-5 guidelines, MUST calculation)
- Patients who have identified a caregiver
- Patients and family members are informed of the diagnosis and the objectives of the therapies and who have reported awareness of the disease phase (evaluated by the palliative doctor).

Exclusion criteria

- Patients with prognosis less than three months to enable the rehabilitative intervention
- Presence of important mental disorder or dementia
- Severe sensory deficit
- Presence of diffuse bone metastases that put the patient at risk of fracture during rehabilitation exercise.

Intervention

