The intervention involves two activities, psycho-educational and rehabilitation. The operators involved in the intervention will receive pre-intervention training and supervision.

Training for operators

The training includes two afternoons of 4 hours each, over a three-week period, during which the main theories on family types will be traced with particular focus on the context of palliative care and the management of the patient / caregiver dyad. The contents will focus on the characteristics and methods of conducting a psycho-educational intervention, specifically related to the cancer cachexia. The theoretical part will be integrated into the practical part through the analysis of clinical cases proposed by nurses and physiotherapists, in particular, with the request to analyze the functioning of the dyads related to food management. This part will be conducted by the PI of the study, Unit of Psycho-Oncology, Scientific Direction, Ausl - IRCSS of Reggio Emilia.

Psycho-educational intervention

The intervention is structured during a face-to-face consultation between a patient–family caregiver dyad and a trained nurses. It is designed to help patient and family caregivers cope with involuntary weight loss and declining appetite by seeking to strengthen individual and dyadic coping resources. The intervention includes 3 weekly meetings for outpatients (Palliative Care Unit, Azienda Usl - IRCSS of Reggio Emilia) which address the following topics consecutively to help patients and their family members talk about weight and eating-related problems and solutions:

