- ‘Mapping to change eating habits tool’ to aid the patient and the family caregiver in talking about their own experience of the patient’s change in weight and eating habits (for example, role of the family caregiver during the preparation of meals, modalities, meanings associated with food, reactions of the patient). The nurse should empower patients and their family carers to understand the nature, course, and biological mechanisms of cachexia and acknowledge its negative effects (e.g., patients’ weight loss, reduced appetite, early satiety). At the end of the meeting, the nurse will collect the main needs reported by the patient and caregiver with respect to both the management of mealtimes and the experiences associated with them and will ask the dyad to observe their own relational dynamics with respect to the role that food takes during the day. To conduct this meeting and collect the data, the nurse uses the tool for evaluating family functioning to construct a first map of the interaction of the dyad.

- Sharing of data collected during the first meeting both by the nurse and the dyad. The nurse will propose practical examples of different ways of managing food in the care of the cancer patient and proposing other ways to support the patient. In particular, the nurse will facilitate talking about each perspective, feelings and food, and how the patient and family carer help each other manage weight and eating related problems. These reflections are embedded in a naturalistic conversation.

- Final reevaluation meeting based on the needs that emerged.

- Proposal of a follow-up meeting to be agreed upon, based on the needs emerged and the clinical condition of the patient.

For the first month, at the end of each meeting and thereafter, as requested by the team, there is a supervision with the PI and Psycho-Oncology Unit, to which the nurses will report what emerged from the interview with the dyad, to set the next meeting based on the shared analysis of the needs that emerged and the interaction methods detected.

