For each participant, basic information will be collected regarding: age, sex, marital status, family unit, education, profession, religious practice, location of the primary tumor, date of diagnosis, KPS, immediately after giving informed consent through these sources:

- direct request to the patient and / or caregiver
- UCP folder
- Matilde computerized file system.

Analysis

The evaluation will be carried out by trained operators who carry out their work outside the clinical area of the study and who will not have contact with the patients and families involved in the study in order to protect the data collection.

Primary objective: for the feasibility, the proportion of number of dyads who completed the intervention / involved dyads will be evaluated. Compliance will be assessed for each individual component (psycho-social and rehabilitative intervention). The overall intervention will be evaluated feasible if there is compliance greater than or equal to 50 percent to both interventions.

Secondary objectives:

The effects of the intervention will be evaluated on:

- quality of life and anorexia-cachexia syndrome related distress: Functional Assessment of Anorexia-Cachexia Therapy (FAACT)
- caregiver burden: Zarit Burden Scale

- family functioning in the palliative care setting: Family Functioning index
- physical performance Superior Arts: Hand-Grip strength test
- physical performance Lower Arts: 30 seconds sit-to stand test
- adherence to each of the two components (psycho-educational and rehabilitative) through participation in meetings and clinical diaries
- acceptability of the intervention through ad-hoc semi-structured interviews.

Measurement Scale

- Functional Assessment of Anorexia-Cachexia Therapy (FAACT)^{26,27}

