- Ad-hoc semi-structured interviews aimed at the dyad one month after the intervention. The interviews will be conducted by a research nurse ([name]) trained in qualitative research and focus groups and by the PI of the study for a total of 7 interviews. The dyads will be chosen on the basis of pre and post intervention results, with particular attention to identifying the participants who have reported good adherence to the intervention and participants who have reported difficulties.

- Ad hoc semi-structured interviews with nurses and physiotherapists who participated in the study. The interviews will be conducted by the research nurse ([name]) and by the PI of the study for a total of 4 interviews corresponding to the operators involved (2 nurses and 2 physiotherapists).

Data analysis

The data analysis will be conducted by the Clinical and Statistical Studies Unit - IRCCS Reggio Emilia.

Sample size: since it is a pilot study to collect data on the feasibility of the intervention, the formal calculation is not carried out but is identified in 30 patients, according to criteria of opportunity and feasibility, the sample for the main objective. The statistical analysis will be descriptive: the primary endpoint will be represented with descriptive statistics tools (average, median, minimum, maximum, remarkable percentiles, central tendency index (with 95% CI), standard deviation, shape indexes.

secondary endpoints: descriptive representation (for T0, T1, T2 and T3) of the endpoints and of the variations detected between T0 and T3.

Ethical considerations

Access to clinical documentation

The researchers responsible for completing the Basic Information Sheet (Annex 11 Evaluation Scales) will collect only the data contained in the form (personal data and clinical data), by consulting the clinical documentation held by the Palliative Care Unit (Azienda USL - IRCCS of Reggio Emilia). The information collected will be limited to those contained in the form and aimed at carrying out psycho-educational and rehabilitative interventions. Please note that, to protect the privacy of all those involved:

- it is expected that the names of the dyad (patient / caregiver) will appear only in the aforementioned form, combined with a code
- in all the remaining forms, the patient will be identified exclusively with a code

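### The PI, who trains the operators and supervises the nurses, is also a named interviewer for the four operator interviews on acceptability

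*Combined protocol and SAP*

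**What the plan says.** Objectives of the Study puts acceptability among the secondary aims: "Secondary objective: improve the quality of life of patient and caregiver, acceptability of the intervention". The Analysis section assigns one measure to it: "acceptability of the intervention through ad-hoc semi-structured interviews". The Measurement Scale section then describes two sets of such interviews, 7 with dyads and 4 with operators. The operator set is to be conducted by a research nurse and "by the PI of the study for a total of 4 interviews corresponding to the operators involved", counted as 2 nurses and 2 physiotherapists. The text does not say whether the two interviewers sit together or share the interviews out. The item on the dyad interviews describes the research nurse as trained in qualitative research.

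The PI has two other roles towards these operators:

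- **Training.** Under Training for operators, the practical work rests on "the analysis of clinical cases proposed by nurses and physiotherapists". The closing sentence of that section begins "This part will be conducted by the PI of the study".
- **Supervision.** Under Psycho-educational intervention, "there is a supervision with the PI and Psycho-Oncology Unit", "to which the nurses will report what emerged from the interview with the dyad". It follows each meeting during the first month and afterwards takes place when the team asks for it. The next meeting with the dyad is planned from that discussion.

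**The concern.** An interview on acceptability is useful only if the person interviewed feels free to say that the intervention was awkward, burdensome or badly received. Here one of the two named interviewers taught the operators at least part of what they deliver and, for the nurses, helped plan how each dyad meeting should go. Criticism of the intervention may then be criticism of the interviewer's own work, and the likely direction of any distortion is favourable.

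What is at stake is the operators' account of acceptability. The section on what the study contributes looks ahead to later work, with the aim of "estimating the effect of the intervention for a future multicenter efficacy study". An over-favourable account could carry a delivery problem into that larger study. The primary objective rests on completion and compliance, which these interviews do not feed.

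**Working it through.** No power or sample-size formula applies: the Data analysis section calls the study a descriptive pilot and sets 30 patients without a formal calculation. The check is a count of who is linked to the PI, set against who is interviewed.

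**1. The plan's own figure.** 2 nurses + 2 physiotherapists = 4 operator interviews. This agrees with the stated 4, so the set is every operator involved and not a sample of them.

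**2. Training link.** The closing sentence of Training for operators may refer to the practical case work only or to the whole training. Both professions bring cases to the practical work, and all operators receive the training. On either reading the link covers 2 + 2 = 4 of 4.

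**3. Supervision link.** The arrangement is described only for the nurses: 2 of 4. The opening of the Intervention section promises training and supervision to all operators, but gives no detail of any supervision for the physiotherapists. So 2 of 4 are established, and up to 4 of 4 are possible.

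| Operators | Number | PI-led training | Supervision involving the PI |
|---|---|---|---|
| Nurses | 2 | yes | yes |
| Physiotherapists | 2 | yes | promised in general terms, not described |

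**4. Interviews in which the PI takes part.** If the two interviewers work jointly, 4 of 4. If they divide the interviews, with each taking at least one, the PI takes between 1 and 3. In that case the number of nurses interviewed by the PI lies between 0 (the PI sees physiotherapists only) and 2. The plan allows all of these.

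**5. Weight of one guarded answer.** Each operator supplies 1/4 = 25% of the operator interviews. The operator set is 4/(7 + 4) = 4/11, or 36%, of all planned interviews.

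**6. Size of bias.** The documents give nothing from which to estimate how much less frank an operator would be. No figure can be attached.

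**The case against.** The strongest reply is that the links are thinner than they look. Routine supervision is limited to the first month and shared with the Psycho-Oncology Unit. If that month is the first of the study (my assumption; the text does not say), it covers about 1 of the 12 months of recruitment. The training is two afternoons of 4 hours. Nothing describes the PI as the operators' line manager: what is described is case supervision. The PI is not the sole interviewer. The Ethical considerations section also promises that published data will not be traceable to an individual professional. All of this stands and lowers the weight of the point. It does not remove it, because the PI remains a named interviewer of people the PI trained, and the confidentiality promise covers presentation and publication, not the interview itself.

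It can also be said that other data bear on acceptability. Reasons for refusal are kept, patients note in a diary what stopped them finishing the exercise programme, and adherence to each component is measured. These could contradict a favourable account. However, the plan does not assign them to acceptability, and refusal reasons and patient diaries do not carry the operators' view.

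Two stronger readings are tempting but not supported:

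- A reader might infer that choosing dyads on pre and post results shuts out those without a T3 assessment. No text requires T3 data for selection. The T0-to-T3 wording belongs to the descriptive analysis, and hand-grip, sit-to-stand and session counts exist before T3. The selection already looks to adherence and to participants who reported difficulties.
- A reader might infer that the PI should also be kept out of the 7 dyad interviews. The PI's described link to the dyads before those interviews is indirect, through supervision of the nurses. That is too little to support the change.

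**Conclusion.** The point holds as a cheap improvement. A secondary objective measured only by interview has, for its operator part, a named interviewer who trained all 4 operators in at least part of the work and who is described as a supervisor of 2 of them. The risk is of answers that are too favourable, greatest for the nurses.

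The exposure is at most 4 of 4 interviews. A reader might infer that the PI is present at all four, but the plan does not say so. Nor is it established that the physiotherapists have the training link alone, since supervision is promised to all operators. The size of any bias is unknown, and the primary feasibility proportion is unaffected.

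The conclusion rests on two assumptions: that the operator interviews serve the acceptability objective, since the plan gives them no other purpose, and that people tend to be more guarded with someone who trained or supervised them.

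**What to change.** In the Measurement Scale item on operator interviews, state that the research nurse already named there conducts all 4 interviews without the PI. The number of interviews and the arrangements for the 7 dyad interviews stay as they are.

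The cost is a change of wording and a re-allocation of work, with no new staff role. There are three downsides. The research nurse takes on somewhat more work, and the documents state neither capacity for it nor independence from the care team; the sponsor should confirm both. The PI's knowledge of the intervention is lost in those interviews. With only 2 operators per profession, the PI may still recognise who said what in the reported material, so the change reduces the problem without removing it.
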